BACKGROUND AND SIGNIFICANCE

Polycystic ovary syndrome (PCOS): PCOS, a common endocrinopathy affecting 6–10% of women, manifests by hyperandrogenism, ovulatory dysfunction and polycystic ovaries (PCO) in its complete phenotype. Abdominal adiposity occurs frequently in PCOS women vs. controls, including some, but not all, nonobese individuals. Consequently, the estimated prevalence of MBS in PCOS is 33-47%, about 2-3 times higher than that of age-matched controls.

Interplay between adipose function and androgen excess: In PCOS, intrinsic defects combine with endocrine factors to impair insulin sensitivity and induce adipocyte insulin resistance (IR). Conversely, physiological androgen administration to women induces IR. In PCOS women, therefore, androgen excess could decrease numbers of SC abdominal adipocytes and reduce capacity of this adipose to safely store fat. Thus, if energy intake exceeds this capacity, SC abdominal adipocytes would likely overfill with lipid to promote ectopic lipid deposition. We hypothesize that PCOS-related hyperandrogenism decreases adipogenic differentiation and increases adipocyte lipid content in a constrained SC abdominal adipose, inducing lipotoxicity, IR and ovulatory dysfunction.

Therefore, reducing PCOS-related androgen excess could improve SC abdominal adipogenic function and ovarian folliculogenesis, reducing use of ovulation-inducing agents in PCOS women wishing to conceive, and risks of multiple pregnancy.

Effect of flutamide on PCOS: Administration of flutamide, a nonsteroidal anti-androgen, to PCOS women lowers circulating androgen and triglycerides levels. Flutamide also restores ovulation in some, but not all, PCOS women. We will systematically compare SC abdominal adipogenesis, circulating adipogenic markers and SC abdominal as well as visceral (omental plus mesenteric) adipose content of lean PCOS women randomized to 6-month low-dose flutamide vs. placebo to determine how differences in key variables affect ovarian function and morphology, as well as in vivo E2 responsiveness to FSH.

We also are able to quantify SC abdominal and visceral adipose content by magnetic resonance imaging (MRI), as performed by [name]. Finally low-dose flutamide vs, placebo administration to lean PCOS women will discover novel molecular and biochemical markers that predict efficacy of androgen blockade in restoring adipogenic and ovarian function.

AIMS AND OBJECTIVES

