If a woman becomes pregnant while participating in this study she will be excluded from further participation.

Non-English speaking individuals will be excluded from this study. The eligibility criteria includes non-Hispanic Caucasians only so it is assumed that the vast majority of participants will be English speaking. Since PCOS phenotype varies by ethnicity, eligibility was restricted to only one ethnic group in order to control for ethnic variability.

SUBJECT IDENTIFICATION AND RECRUITMENT

Initial contact may be made at the time the patient visits the clinic for non-research related indications. The treating physician, colleague physician, nurse, medical assistant or study coordinator will interface with the potential subject to obtain their consent to be contacted regarding the study. In addition, IRB approved scripts for contact recruitment, responding by e-mail, in person contact or referral contact will be used.

Additionally, patients will be recruited by obtaining a list of possibly eligible patients by extraction of electronic medical records as described in the "Review of Medical Records" section below. After reviewing their charts, verifying eligibility, and obtaining approval from their PCP or GYN provider, patients will be directly contacted by a member of the study team using the IRB approved screening script.

Since potential subjects may contact us directly in response to flyers, ads, etc., we will respond to all inquiries via phone or email as they prefer. If a potential participant contacts us directly by email and wishes more information without phone contact, the consent form will be sent to them via email for their consideration. If they are interested in the study, they will have the option to respond by phone for further screening. The study team will utilize the recruitment script/screening script. The recruitment script/screening script will not be sent via email to potential subjects.

Subjects who have already undergone an OGTT test will be contacted at their next

study visit or by phone to be given the opportunity to undergo FSIGT testing.

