The study procedures will take place at UCLA Westwood Campus in the 200 and 300 Medical Plaza Buildings, the Clinical Translational Research Center, Ronald Reagan Medical Center, and/or Room 22-265 in the Center for Health Sciences.

Before subjects begin the study:

Before they begin the study, subjects will need to agree to use a non-hormone type of

Revised 3-7-18 UCLA IRB #12-001780 Page 12 of 27

birth control for the duration of their participation in this study. If subjects have not undergone permanent sterilization, examples of acceptable types of birth control are an IUD (without hormones) or spermicidal jelly in combination with a diaphragm or condoms.

During the study:

If subjects take part in this study, the researcher(s) will ask them to do the following:

All Study Participants

Initial Visit

• The consent form will be reviewed with the subject and anyone they wish to have present. If they choose to participate, they will sign the consent form and HIPAA Authorization form. Subjects will be given a copy for their records.

The doctor will ask questions regarding their past medical history, family medical history, and lifestyle to determine if they are eligible to participate in this study.
If subjects are not eligible to participate in this study, no further study related office visits or procedures will be performed and they will receive \$10 for their time
If subjects are eligible to participate, they will undergo the following:

- Physical Exam
- An assessment of their skin
- Height, weight, waist and hip measurements
- Transvaginal ultrasound of their ovaries
- Blood tests approximately 1 teaspoon (6 ml) of blood will be drawn from their vein. All of the blood samples in this study will be used to detect any abnormal hormone levels. A pregnancy test will also be performed.
- Complete questionnaires regarding their feelings about various areas of their health, quality their life, and family history of PCOS and/or diabetes. Subjects have the right to refuse to answer any questions that they do not wish to answer.
- \circ Whether subjects are eligible or not, they will be paid \$20 for completing this visit.
 - It is estimated that this visit will take approximately 2 hours.

Women with and without PCOS

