• Complete a diary regarding what time they took the pill, whether they had any menstrual bleeding, any changes in their health, any medications they took, if they exercised that day, and a brief summary of their diet.

• Collect a sample of their first morning urine once a week and store it until their next clinic visit. Subjects will be given instructions on the collection and storage of the samples.

• Return to the UCLA Clinic once a month for the following:

o A brief physical exam including a measurement of their height, weight, waist, and hips. Review any symptoms subjects may have experienced during the past month.

o Bring their prescription bottles so that the pills can be counted.

o Bring their weekly urine samples.

o Bring their completed diaries.

o Have blood tests (serum pregnancy test, complete blood count, and comprehensive metabolic panel) – approximately 1 teaspoon (5 ml) of blood will be drawn.

o After the third and sixth cycle, subjects will be asked to complete questionnaires regarding their feelings about various areas of their health and the quality of their life. Subjects have the right to refuse to answer any questions that they do not wish to answer. • After the third and sixth cycle, subjects will also have an assessment of their skin, and a transvaginal ultrasound of their ovaries.

• It is estimated that each of these visits will take approximately 1 hour

• Subjects will receive be reimbursed for their parking expenses and receive \$240after all 6 visits have been completed.

• Subjects will be asked to continue taking the flutamide or placebo until the procedures listed below are completed. Every effort will be made to complete all study visits as soon as possible.

After Completing Flutamide/Placebo

The FSIGT, MRI, DXA, Removal of Abdominal Fat, and FSH tests will be repeated as described above. Please note that a testosterone blood test, complete blood count, and comprehensive metabolic panel will be performed at the post-treatment FSH test.

30 Days after Last Pill

o Physical Exam

o Blood tests (pregnancy test, complete blood count, and comprehensive metabolic panel) - approximately 1 teaspoon (6 ml) of blood will be drawn from their vein.

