MRI scanning is painless but they might experience discomfort in the machine. In particular, loud beeping and hammering noises occur during the study when the

scanner is collecting measurements. Subjects also may be bothered by feelings of claustrophobia when placed inside the MRI, or by lying in one position for a long time. Subjects might also experience stimulation of the nerves in their body, which feels like a gentle tap or sensation of mild electric shock.

Because the risks to a fetus from MRI are unknown, subjects cannot participate in this study if they are pregnant.

Known Reproductive Risks:

Subjects should not become pregnant while on this study because the drugs in this study and the DXA scan can affect an unborn baby. Women should not breastfeed a baby while on this study. Therefore, subjects will need to use effective birth control while on this study. Examples of acceptable types of birth control are a diaphragm with spermicidal jelly, condoms, or an IUD (without hormones). Subjects should use birth control starting at the beginning of their participation in this study.

Unknown Risks to Women of Child Bearing Potential and Pregnant Women:

Flutamide can occasionally induce ovulation in a woman with PCOS who does not ovulate. This is important because this medication blocks androgen action and can impair the ability of androgen to normally induce development of the external genitalia in the male fetus. For this reason, if subjects believe that they are pregnant or have a chance of becoming pregnant they should not participate in this study. A serum pregnancy test will be performed before the start of study procedures and monthly throughout their participation in this study. If they are pregnant, the will not be allowed to participate in the study. If women do participate in this study, they must use a medically effective form of birth control before entering the study, while participating in the study, and for at least one month after stopping the study. If they become pregnant during the study, they will be asked to tell the researchers right away.

Unknown Risks to Infants:

The side effects of Flutamide on infants are not known, therefore if women are currently breastfeeding they cannot participate in this study.

Loss of Confidentiality:

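### The protocol tests for pregnancy on study drug and names a hazard to the male fetus, but its rules do not collect the outcome of a drug-exposed pregnancy

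*Combined protocol and SAP*

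**What the plan says.** **The hazard.** Under Potential Risks (unknown risks to women of child-bearing potential) the protocol states that "this medication blocks androgen action and can impair the ability of androgen to normally induce development of the external genitalia in the male fetus". The same paragraph says that "Flutamide can occasionally induce ovulation in a woman with PCOS who does not ovulate", and Background and Significance agrees: "Flutamide also restores ovulation in some, but not all, PCOS women".

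**Detection.** At the Initial Visit, "A pregnancy test will also be performed". The monthly visits on drug include "Have blood tests (serum pregnancy test, complete blood count, and comprehensive metabolic panel", and the visit 30 days after the last pill repeats "Blood tests (pregnancy test, complete blood count, and comprehensive metabolic panel". Self-report is also requested: "If they become pregnant during the study, they will be asked to tell the researchers right away". Non-hormonal contraception is required during the study and for at least a month afterwards.

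**Action.** Exclusion Criteria: "If a woman becomes pregnant while participating in this study she will be excluded from further participation". Pregnancy is also item 9 under Rules for Withdrawing Participants from Study Interventions. That heading refers to interventions, but the sentence introducing the list speaks of leaving the study.

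**Later contact.** The Aim 2 methods and the end of Procedures describe a call six months after procedures are completed, to participants who received flutamide or placebo. It asks about health problems, or a pregnancy, arising after that completion.

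**The concern.** The protocol foresees conception on drug. It expects ovulation to return in some women, bars hormonal contraception, and tests repeatedly. It also says which harm to look for. Once a pregnancy is found, the only stated action is removal, and the one later contact is worded around pregnancies that begin after the study work is done. Neither step yields the information that would show whether the named harm occurred.

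The contrast with other toxicity is instructive. Under Potential Risks, a grade 3 or higher toxicity stops the drug and starts weekly blood tests until values normalise. That harm is followed to its end; a pregnancy is not. What is at stake is safety capture only. No aim, endpoint or efficacy analysis depends on it.

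**Working it through.** The protocol states no figure on this point, so there is none to reproduce. The check counts the tests, sets the provisions side by side, and traces what happens to a pregnant participant.

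**1. Tests itemised for a woman who completes dosing (Procedures).** Initial visit 1 + monthly visits 6 + 30-day visit 1 = 8, of which 6 + 1 = 7 follow the first pill. More may be due, because the risk section calls for monthly testing for as long as she participates, and dosing continues past cycle 6 until the end-of-treatment tests are finished.

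**2. Time at risk for a completer.** Dosing lasts at least 6 × 28 = 168 days; adding the 30 days after the last pill gives at least 168 + 30 = 198 days. A woman withdrawn for pregnancy stops sooner.

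**3. What each provision collects about a pregnancy.**

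| Provision | Content | Outcome or newborn item |
|---|---|---|
| Self-report (Potential Risks) | That she is pregnant | None |
| Exclusion Criteria | Ends participation | None |
| Withdrawal list, item 9 | Ends intervention, or study; heading and lead-in differ | None |
| 30-day visit | Pregnancy test | None |
| Six-month call | Health problems or pregnancy since completion | None |
| Data and Safety Monitoring Plan | Monthly review of adverse events; pregnancy not mentioned | None |
| Stopping Rules | Hepatic events only | None |

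**4. Three women traced through these rules.**
- *Conceives during dosing, positive at a monthly visit.* She is excluded. The text does not say whether she still gets the call. If she does, her pregnancy predates completion and falls outside the pregnancy question.
- *Conceives near the last pill, positive at the 30-day visit.* She may be called, and could volunteer information under health problems. If completion means the end-of-treatment tests, a later conception would fall within the pregnancy question, but that question asks only whether she became pregnant.
- *Conceives between the initial test and the first pill.* The additional bloods listed before dosing are a blood count and a metabolic panel; no pregnancy test is named there. She may start the drug pregnant, test positive at a monthly visit, and then follow the first path.

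**5. Timing of the call.** Assume birth about 266 days after conception and six months ≈ 183 days; neither day count is in the protocol.
- Conception on the day of the last pill, call counted from the 30-day visit: 30 + 183 = 213 days after conception, or 266 − 213 = 53 days before birth. The call precedes any birth later than day 213.
- Call counted from withdrawal, with the pregnancy found 28 to 56 days after conception: 28 + 183 = 211 to 56 + 183 = 239 days, also before day 266.

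In these cases the call would come too early to learn about the newborn, even if it asked.

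**6. Women in scope.** The plan expects 36 PCOS completers and recruits at most 70, across both arms. The allocation ratio is not stated; if it were equal, the flutamide arm would be 36/2 = 18 to 70/2 = 35 women. Some recruits may never take a pill, because baseline testing and biopsy come before dosing.

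**The case against.** The strongest objection is that silence in an incomplete text proves little. The consent pages and a part of the protocol were not available, and pregnancy instructions could sit there. This stands as a limit. It is softened because Procedures and Potential Risks both say that they reproduce the consent form, and neither contains such a follow-up.

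Second, much is already in place: contraception, monthly testing, prompt self-report, monthly adverse-event review, an unaffiliated physician monitor, and a call whose description does not expressly leave out women withdrawn early. These limit exposure and provide a channel for reporting, but none asks how a pregnancy ended.

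Third, the withdrawal list can be read as ending study treatment only, as its heading suggests and as its item on hypertension says explicitly. That reading is reasonable. The sentence in Exclusion Criteria is broader, however, and the two should agree.

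Four stronger inferences are tempting and should not be drawn:
- A reader might infer that every PCOS participant has 8 tests and at least 198 days at risk. Both figures hold only for women who complete dosing, and a woman withdrawn for pregnancy does not.
- A reader might take 36 to 70 as the number exposed to flutamide. It spans both arms, and 70 counts recruits, not women dosed.
- A reader might infer that the protocol forbids contact after exclusion. It does not; it simply requires none.
- A reader might infer that a material number of affected pregnancies is likely. The protocol gives no pregnancy or contraceptive-failure rate, and the number may be zero.

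**Conclusion.** The point holds as a gap in safety capture. The protocol names a fetal hazard and tests for the exposure, but its rules, followed as written, do not collect the outcome of a drug-exposed pregnancy: 8 itemised tests for a completer, and no scheduled item on pregnancy or newborn outcome for anyone. This is more than missing detail, because the exclusion rule and the wording of the call steer around the pregnancies that matter.

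Its size in events cannot be stated. The flutamide-exposed group is smaller than the 36 to 70 PCOS women in both arms, and no efficacy result changes. The conclusion assumes that the unavailable pages contain no pregnancy follow-up. The timing argument also assumes a usual length of gestation, but the finding does not depend on it. It calls for a cheap improvement and does not challenge the design.

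**What to change.** 1. In Exclusion Criteria and in item 9 of the withdrawal rules, say that pregnancy ends study drug and study procedures only.
2. Beside the six-month call (Aim 2 methods and the end of Procedures), add, with the woman's consent, one phone contact after the expected delivery date. It should cover any woman, in either arm, whose pregnancy overlapped study drug or began within 30 days after her last pill, including conception before the first pill. The 30 days match the final test visit and roughly match the contraception requirement.
3. Record her report of pregnancy outcome and newborn status, including external genitalia. Send it to the IRB and to the existing unaffiliated monitor.

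The cost is one call per exposed pregnancy, plus consent and authorization wording for information about the newborn. No visit, sample, procedure, randomization step or analysis changes. The report would be unverified, and one such report in a trial of this size could raise a concern but could rarely settle whether the drug caused it.

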• The first blood draw will be sent to the laboratory for an immediate test of their progesterone level which indicates whether or not they are ovulating. If the progesterone test indicates that they are ovulating, the FSH test will not be able to be performed that day and will need to be rescheduled. If the test cannot be performed, they will be paid \$10 for this visit and another appointment will be scheduled.

• It will be necessary for them to stay at UCLA Medical Center in the Clinical Translational Research Center, which is located in the Center for Health Sciences building for approximately 26 hours in order to complete this test. Food will be provided to them during the testing.

• Approximately 1-2 tablespoons (21 mL) of blood will be drawn from their vein.

If subjects have PCOS, an additional 4 mL (approximately 1 teaspoon) of blood will be drawn for a complete blood count and comprehensive metabolic panel in order to assure that there are no abnormalities in these blood values before they begin taking flutamide or placebo.

Since some of the blood tests to confirm hormonal levels are timed around different phases of the menstrual cycle and menstrual cycles vary, it is possible some of the blood tests described above will need to be repeated. The Frequently Sampled

Intravenous Glucose Tolerance Test and the Follicle Stimulating Hormone Test will only be performed as described above.

Subjects will be paid \$280 once they have completed the FSIGT, DXA, MRI, Fat Removal, and FSH stimulation visits. If they report to UCLA for a study visit and their blood tests indicate that they are not in the desired part of their menstrual cycle for a particular test, they will be compensated an additional \$10 and the visit will be rescheduled. Participants will be asked to complete a form so that a check can be mailed to them within 2 months.

Women who do not have PCOS will conclude their participation in this study at this point. No further procedures for this study will be conducted.

Women with PCOS will continue participation as described below.

Women with PCOS will be asked to do the following:

• Take one pill (either placebo or flutamide) each morning before breakfast for 6 complete 28 day cycles. The drug flutamide has not been approved by the FDA for use in women or for the treatment of PCOS.

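### The monthly pregnancy-test rule is not carried into the baseline visits, and the first pill is not tied to a current negative result

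*Combined protocol and SAP*

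**What the plan says.** Three parts of the protocol bear on this.

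- **Entry.** The Initial Visit list under PROCEDURES includes, with the blood tests, "A pregnancy test will also be performed".
- **General rule.** Under POTENTIAL RISKS, in the paragraph on women of child-bearing potential: "A serum pregnancy test will be performed before the start of study procedures and monthly throughout their participation in this study". The next sentence bars pregnant women: "If they are pregnant, the will not be allowed to participate in the study".
- **Visit schedule.** After entry come the FSIGT, the MRI and DXA scans, the fat removal and the FSH stimulation test. At the FSH visit, PCOS women have "an additional 4 mL (approximately 1 teaspoon) of blood will be drawn for a complete blood count and comprehensive metabolic panel", with the stated aim of excluding abnormal values before drug or placebo starts. Once they are taking pills, the monthly visit reads "Have blood tests (serum pregnancy test, complete blood count, and comprehensive metabolic panel". A pregnancy test is listed again 30 days after the last pill.

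The schedule also allows for delay. If progesterone suggests ovulation, "the FSH test will not be able to be performed that day and will need to be rescheduled", and because of cycle timing "it is possible some of the blood tests described above will need to be repeated". The introduction to PROCEDURES says that the order of procedures may change.

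**The concern.** The draw at the FSH visit is the protocol's own safety check before drug. Its two assays reappear in the monthly on-drug panel with a serum pregnancy test added. The pregnancy test is therefore the one item of that panel not listed before the first dose.

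The stake is fetal safety. POTENTIAL RISKS says that flutamide may bring on ovulation in women who were not ovulating, and that blocking androgen action can interfere with genital development in a male fetus. Pregnancy bars entry and ends participation, but those rules work only if a pregnancy is found. A woman who conceives during baseline could begin daily drug on an out-of-date negative result. PCOS women are studied during amenorrhea. That makes conception less likely, but it also means that a missed period would not give warning.

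**Working it through.** The plan states no figure on this point, so the check sets every listed pregnancy test against the visit sequence.

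| Point in the study | Pregnancy test listed | Other relevant check listed |
|---|---|---|
| Initial visit | Yes | Ovarian ultrasound |
| FSIGT | No | Progesterone, required |
| MRI and DXA | No | Progesterone, optional |
| Fat removal | No | Progesterone, optional |
| FSH test | No | Progesterone, required; ovarian ultrasound; blood count and metabolic panel |
| First pill | No dispensing visit described | None |
| Monthly visits on drug (6) | Yes, each | Blood count and metabolic panel |
| 30 days after last pill | Yes | Blood count and metabolic panel |

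**Count.** Listed tests are 1 (entry) + 0 (four baseline visits) + 6 (monthly) + 1 (30 days after) = 8. Only the entry test comes before drug.

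**How old can the last result be at the first pill?** Let *a* be its age in days at the first pill, and *d* the days on drug until the next test. Take a month as one 28-day cycle (an assumption; the protocol uses both terms).

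- *General rule followed literally.* Two successive tests are at most about 28 days apart, so *a* + *d* ≤ about 28. The result may be up to about a month old at the first pill. A newer result leaves more days on drug before the next test, up to about 28.
- *Only the itemised visits followed.* *a* is the whole time from the initial visit to the first pill. The documents set no limit on it, and rescheduling lengthens it. *d* is about 28, because the next listed test is at the first monthly visit.

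**Does the general rule reach baseline?** Yes, on the protocol's own use of the word. PROCEDURES says that controls conclude their participation once baseline testing is done, so participation includes baseline. But the LAY SUMMARY and PROCEDURES place the monthly visits in the period of pill-taking, and no pre-drug visit puts the rule into effect.

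**Is dispensing conditional on a result?** No text says so. The general rule sets a frequency. The ban on pregnant women sets a consequence. Neither requires a negative result in hand when the first pill is given.

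The delay also has an awkward feature. Rescheduling is triggered by signs of ovulation, which is when conception is possible, and the listed response is a new appointment rather than a pregnancy test.

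**The case against.** A reader might infer that the protocol omits pregnancy testing before drug, or that it sets no limit at all on the age of the result. The documents do not support either reading. A test at entry is listed, pregnant women are barred, and "A serum pregnancy test will be performed before the start of study procedures and monthly throughout their participation in this study" taken at its word puts a test within about a month of the first pill. This part of the objection stands, and it narrows the point to a rule that the schedule does not carry out and a dispensing step with no condition attached.

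Other safeguards are also real. Non-hormonal contraception is agreed before the study begins. Progesterone is mandatory at the FSH visit, with an immediate result, and a level suggesting ovulation stops that test. An ovarian ultrasound is listed for the same visit, which in the listed order is the last before pills start. Women must report a pregnancy at once. A pregnancy that goes unnoticed into dosing would need several of these to fail together. Still, progesterone is specified as an ovulation check and the ultrasound as an ovarian assessment; neither is specified as a pregnancy test. The order of visits is not fixed. Contraception is also required on drug, where the protocol nevertheless tests every month.

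Finally, silence in the schedule is limited evidence. PROCEDURES presents the list as an outline taken from the consent form, dispensing is not described, and a stretch of text before the inclusion criteria was not available for this check. The finding is therefore that the test is not listed or required at that point, not that it was not done.

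**Conclusion.** The point holds in this narrow form. The protocol requires pregnancy testing before study procedures and monthly, but the baseline visits do not carry that rule, the pre-drug safety draw omits the test, and no negative result is required when the first pill is dispensed. The last result could be about a month old if the general rule is followed, or older by an unstated amount if only the itemised visits are followed.

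No number of exposed pregnancies can be given, because the documents supply neither the entry-to-first-pill interval nor a conception rate. With contraception and the progesterone check in place the probability is presumably low, but the harm that the protocol itself names is serious. The change should be made for participant safety; it bears on no endpoint, estimate or analysis. Confidence is medium, because dispensing procedures outside the available text may already include such a check.

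**What to change.** In PROCEDURES, add a serum pregnancy test to the pre-drug draw at the FSH visit for PCOS women. State that the first pill is dispensed only on a current negative result, whatever the order of procedures, and give the result's maximum age. Seven days is a proposal made here; the documents offer no figure.

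Two optional clarifications would bring the schedule into line with the general rule: list a pregnancy test for women who stay on drug after cycle 6 while end-of-treatment tests are completed, and run one before DXA when blood is already being drawn for progesterone.

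The cost is one amendment, one extra assay on an existing draw and a short wait for the result. The FSH visit lasts about 26 hours and already relies on an immediate laboratory result, so the wait should be easy to absorb. If dispensing is delayed past the limit, the test must be repeated. A very early conception could still be missed, so the monthly tests on drug must stay.
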